reviewed with teens under the age of 18. The parent and participant will understand that refusal to participate will not influence their ability to receive treatment at CCHMC and that they are free to withdraw at any time. After signing the consent and assent form, parents will be given a copy of the signed consent/assent forms to take home with them. Parents who consent to participate will then be interviewed and complete rating scales while the teen is administered the initial assessment battery (diagnostic interview, IQ testing, etc.). Teens will also complete a simulated driving assessment and a road test. Teens meeting inclusion criteria will then be randomized to either the FOCAL+ or the sham intervention group.

The two intervention arms will be equal in sample size. Hypothesis testing will require 68 participants in each arm (see Power Analyses, Section 5.f.2.a.1). Randomization will be stratified by gender and months of driving experience to ensure that there is equal representation of gender and months of driving experience across groups.

Teen participants and their parent will participate in an initial training and then 4 subsequent weekly trainings. At each of the 4 subsequent weekly training sessions, they will first complete a simulated driving assessment and then engage in a session of either FOCAL+ or the sham intervention training.

At the final training session 1-month post-randomization and then again at 4-, 8- and 12-months post-randomization, they will again complete the simulated driving assessment and road test. In addition, teens' naturalistic driving will be assessed using an in-car DriveCam monitoring system for a full year or their entire tenure in the study.

Participant Retention

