The PI will continuously evaluate the project's performance, safety, treatment fidelity, and need to stop. Performance will be monitored by examining subject recruitment, comparison with targeted recruitment retention, protocol adherence, and quality of data collection procedures. This will primarily be accomplished in weekly staff meetings attended by the PI. Any deviation in achieving recruitment targets will be reported to the NIMH program officer. In order to assure intervention fidelity, the PI will randomly attend training sessions. In order to assure the accuracy of data entry, all data will be verified by double entering all data into our Microsoft Access database. Inaccuracies will be addressed by double-checking the report forms. If inaccuracies cannot be resolved by checking the source forms, we will review that patient's chart again at the next data collection visit in order to resolve the query.

Should any adverse event occur, we have established a set of protocols and procedures to manage the handling/reporting of such events. Adverse event monitoring will occur at each assessment visit. Participants will be asked if they have had any adverse experiences since the last visit. Adverse events leading to discontinuation will be documented. All serious adverse events (SAEs) will be reported to the CCHMC Institutional Review Board (IRB) according to the regulations set forth by this IRB, as well as to the NIMH. All staff will be trained to identify adverse events and on procedures for handling them (e.g., reporting of child abuse, suicidality, HIPPA training, human subjects training, etc.).

The PI, [name], is ultimately responsible for ensuring the safety of participants enrolled in the protocol. Following baseline evaluation, [name] will be ultimately responsible for making the decision for particular participants to continue or discontinue in the protocol.

6.f ClinicalTrials.gov Requirements

This clinical trial will be registered with ClinicalTrials.gov.

INCLUSION OF WOMEN AND MINORITIES

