6.4 Study Assessments

Frequency and Timing of Relevant Assessments:

	Baseline/Randomization	1-month follow-up assessment	6-month follow-up assessment	12-month follow-up
Diagnostic and Clinical Assessment	X			
Driving Simulation Assessment		X (2 runs)	X (2 runs)	
DriveCam Recording	X (Installation)	← CONTINUOUS →		
Driving Records		← CONTINUOUS →		
Adverse event monitoring		← CONTINUOUS →		

Analysis Time Windows:

Visit (target day)	Lower bound (days)	Upper bound (days)
Baseline/Diagnostic and Clinical Assessment (-7)	-14	-7
Randomization/Training 1 (0)	N/A	N/A
Training 2 (7)	4	10
Training 3 (14)	11	17
Training 4 (21)	18	24
Training 5 (28)	25	31
Month 1 (30 post-training 5)	30	45
Month 6 (180 post-training 5)	180	195
Month 12 (360 post-training 5)	Not in person	Not in person

Study Variables:

Primary Endpoint Variables Collected During Secondary Task (ST) Performance Portion of Driving Simulation:

1) Extended eye glances: This variable will be a frequency count of the number of ≥ 2 secs glances. Extended eye glances of interest are those occurring during the ST portions of the drive. The range for this variable could range from 0 to 100.

2) Standard Deviation of Lane Position (SLDP): Standard deviation of lane position will be calculated during the ST portions of the drive. An average of 0 indicates that an individual maintained consistent lane position. The range for this variable is from 0 to 3

Secondary Endpoint Variables Collected using DriveCam:

1) Extended eye glances: As has been done in previous research, the number of ≥ 2 sec eye glances away from the roadway occurring between -5 secs before to 1 sec after the event causing a .6 g-force will be calculated (Dingus, Klauer, Neale et al., 2006). For each event video, we will code the onset and offset of glances away from the roadway. Based on the onset and offset times, we will calculate whether the video clip contains a continuous eye glance away from the roadway that lasts for 2-seconds or longer between -5 secs before to 1 sec after the event. It is possible that some participants will not contribute any data at all to this outcome variable due to not experiencing any .6 g-force events during the 12-month observation. The lower end of the range for this variable for participants who do experience at least 1 .6 g-force event during the observation period is 0. There is no upper limit to this variable.

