8.2.3 Safety Population

All subjects who have a DriveCam installed in their car will be monitored for safety as described in 8.5 Interim Analyses.

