The two outcomes for the secondary analyses, off-road glances and crash/near crash were both measured on a binary scale. Some participants did not have any events either due to the DriveCam not being installed in their car or they did not have any events. Such missing data was not imputed, and we conducted non intent-to-treat analysis using those participants with event data. There was no missing data for the ‘crash/near crash’ secondary outcome across events for those with a DriveCam installed. The GEE analysis for the ‘crash/near crash’ outcome was performed using all

participants with DriveCam event data available. However, long glance data was missing for some events due to unforeseen circumstances (e.g., DriveCam view obstruction or participant driver was wearing sunglasses). Missing data for the 'long-glance' outcome was imputed using GEE model-based imputation. Specifically, a logistic link function was used within a missing data imputation model that allowed the effect of random assignment to predict the presence (=1) or absence (=0) of long-glances nested within participants while controlling for months of driving experience and days DriveCam was operational in vehicle.

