10.6 Secondary Efficacy Analyses

All analyses of secondary endpoint DriveCam data will be analyzed using GEE. GEE analyses assuming a Poisson distribution and natural logarithmic link function will be used to analyze individual DriveCam events per participant (random effect) and assess the relative risk of each dichotomous outcome (i.e., presence/absence of long-glance, crash/near crash per event). For these secondary analyses, relative risk ratios with 95% confidence intervals will be computed rather than testing statistical significance (Zou, 2004). Note that the widths of confidence intervals will not be adjusted for multiple comparisons and no definite conclusions can be drawn from these results.

11 Safety Analyses

The PI ([name]) will be responsible for detecting, documenting, and reporting events that meet the definition of an Adverse Event (AE) or Serious Adverse Event (SAE). Safety data will be tracked and reported as required by Clinicaltrials.gov. Three tables summarizing adverse events will be created:

- All-Cause Mortality: A table of all deaths due to any cause, with number and frequency of such events in each arm/group of the clinical study.
- Serious Adverse Events: A table of all serious adverse events with number and frequency of such events in each arm/group of the clinical study. See Serious Adverse Events definition

below.

- Other (Not Including Serious) Adverse Events: A table of events within any arm of the clinical study with number and frequency of such events in each arm/group of the clinical study. See Adverse Events definition below.

These events will be analyzed and reported for All Randomized Study Participants and by treatment group at the end of the study period. The only SAE that will be analyzed in the interim is events with a shock value (i.e., indicating a collision) as recorded by DriveCam technology (See 8.5 Interim Analyses for more information).

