 2. Further, the SSI-AOD will be checked to see if the 16- or 17-year-old responded affirmatively to critical items on the SSI-AOD reflecting that the teen's substance use may be putting him/her or others at risk for significant harm ("been injured after drinking or using", "been arrested or had other legal problems (such as driving while intoxicated)", or "When drinking or using drugs, are you more likely to do something you wouldn't normally do, such as break rules, break law, sell things that are important to you, or have unprotected sex with someone?"). If so, a clinician will meet with the 16- or 17-year-old to further interview the teen about these items and make a clinical determination if the child is at risk of significant harm to self or others. If so, the parents of the minor will be notified of the issue and the family will be given resources for substance use assessment and treatment in the community.
 3. The SSI-AOD substance use measure will also be collected at the 6-month assessment point. If the teen has a score of 4 or more indicating "Moderate to high substance use and possible need for further assessment", a clinician will meet with

the 16- or 17-year-old child and provide them with resources for substance use assessment and treatment in the community so that they may seek help. We will give the teen the opportunity to insert the information into their phone or have the information emailed to their private email in order that this remains private health information.

At the 12-month timepoint, we will again collect the SSI-AOD but since there is no in-clinic visit, the SSI-AOD will be collected via REDCap survey. The REDCap survey will be programmed so that if the teen has a score of 4 or more indicating “Moderate to high substance use and possible need for further assessment”, the teen will be presented with text indicating that they have scored in the problematic range and providing them with resources for substance use assessment and treatment in the community so that they may seek help.

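### No adverse event question is stated for roughly months 6 to 12 post-training, although the SAP schedules continuous monitoring and promises by-arm mortality, SAE and AE tables for all randomized teens

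*Combined protocol and SAP*

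**What the plan says.** **How AEs are elicited.** Protocol section 6.e states "Adverse event monitoring will occur at each assessment visit" and then "Participants will be asked if they have had any adverse experiences since the last visit". SAP sections 11 to 11.6 define AEs and SAEs and describe the tables, but give no schedule or method for asking about them.

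**When visits occur.** Section 6.a of the protocol places the simulator and road-test assessments "At the final training session 1-month post-randomization and then again at 4-, 8- and 12-months post-randomization". The SAP (sections 6.1 and 6.4) has in-person assessments at baseline and at 1 and 6 months post-training. In the SAP 6.4 visit windows, the row beginning "Month 12 (360 post-training 5" is marked as not in person.

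**What the 12-month contact contains.** SAP 11.5, item 2, says "At the 12-month timepoint, we will again collect the SSI-AOD but since there is no in-clinic visit", and moves that substance-use screen to a REDCap survey. SAP 6.2 and 11.7 send the driving history and medication questionnaires the same way. No other 12-month instrument is listed.

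**What is promised.** The SAP 6.4 schedule shows AE monitoring as continuous. SAP section 11 describes all-cause mortality, SAE and other-AE tables by arm, and adds "These events will be analyzed and reported for All Randomized Study Participants and by treatment group at the end of the study period".

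**What DriveCam covers.** SAP 8.2.3 says "All subjects who have a DriveCam installed in their car will be monitored for safety", by reference to the interim crash review in section 8.5. SAP 8.4 notes: "Some participants did not have any events either due to the DriveCam not being installed in their car".

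**The concern.** The AE question in protocol 6.e was written for a visit schedule that ran through month 12, where asking about the time since the last visit would have covered the whole year. When the later visits were dropped, the substance-use screen was explicitly moved online, but the documents do not show the same being done for AEs. The schedule and the tables nevertheless read as if ascertainment ran to the end of follow-up.

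In a by-arm table whose denominator is every randomized teen, an event nobody asked about looks the same as an event that did not happen. A reader would naturally take the SAE and mortality tables as 12-month data. Crash injury is the harm that matters most here, since the interim safety review exists to detect it, and participants go on driving through the uncovered months. A crash injury in a teen without a camera, or in a car other than the one fitted with it, has no stated active route into the SAE table after month 6.

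**Working it through.** The plan gives no figure to reproduce. The check compares the AE rule with the calendar, then goes through the other possible sources.

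**Inputs (SAP 6.4 visit windows).** Training 5 has target day 28 after randomization. Month 6 has target day 180 after training 5, with an upper bound of day 195. Month 12 has target day 360 after training 5.

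**Length of the period without a stated question** = month-12 day minus month-6 day:
- Month-6 visit on target: 360 − 180 = 180 days.
- Month-6 visit at the upper bound: 360 − 195 = 165 days.

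**Share of follow-up:**
- Post-training origin (360 days): 180/360 = 50%; 165/360 = 46%.
- Randomization origin (28 + 360 = 388 days): 180/388 = 46%; 165/388 = 43%.

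The range is therefore 165 to 180 days, or 43% to 50%.

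**Other sources after month 6, against what the tables need** (death, life threat, hospitalization, disability, as SAP 11.6 defines an SAE):

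| Source | Where stated | What it can show | What it cannot show |
|---|---|---|---|
| Monthly DriveCam shock review | SAP 8.5.1, 8.5.2 | Collisions in camera-equipped cars | Outcome of the injury; events outside that car; any teen without a camera |
| Driving records | SAP 5.1, 6.1, 6.4 | Officially recorded crashes, with or without a camera | Unrecorded crashes; non-crash SAEs |
| 12-month SSI-AOD | SAP 6.2, 11.5 | Injury after drinking or drug use, over the past 6 months | Any other injury, hospitalization or death |
| 12-month driving history and medication questionnaires | SAP 6.2, 11.7 | Driving history such as licensure date; prescribed medication | No AE content is described |
| 24-hour pager | Protocol 6.b | Events a family chooses to report | Anything not volunteered |
| Retention phone contacts | Protocol 6.a | Demographic updates and visit reminders | No AE question is attached |
| Camera de-installation visit | SAP 14.8 (entry of 11/17/2020) | A late in-person contact | No AE question is attached |

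DriveCam keeps 8 seconds before and 4 seconds after a trigger (SAP 5.2), 12 seconds in all, so a clip can show a collision but cannot establish that the teen was admitted to hospital.

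Driving records are also a weak substitute. SAP 14.6 reports 19 crashes from records against more than 100 coded from DriveCam over the same year, and for that reason dropped them as an outcome.

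No source in the table is a systematic query, put to both arms, about hospitalization, non-crash SAEs or death.

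**The case against.** **Months 6 to 12 are not empty.** A reader might infer that DriveCam is the only remaining channel and that every event in a teen without a camera is lost. The documents do not support that. Driving records do not depend on a camera, the SSI-AOD includes an injury item whose recall period matches the gap, and there are pager, telephone and de-installation contacts. What stands is narrower: none of these is described as an AE question.

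**Section 8.2.3 does not restrict the AE tables.** It could be read as confining safety reporting to teens with a camera. It is tied to the section 8.5 crash review, while SAP section 11 sets the table population separately as all randomized participants. The two sections are compatible, but calling the camera group the safety population invites the misreading.

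**Half the calendar is not half the events.** A reader might conclude that about half of post-training SAEs would be missed. That needs a constant hazard, which the documents do not give. Several anticipated AEs in SAP 11.5 (survey discomfort, simulator sickness, medication wash-out) are tied to study visits and sessions and would be concentrated before month 6. The documents also do not say that teens without a camera would be tabulated as event-free, or how many there were.

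**Revised AE text may exist elsewhere.** SAP 14.8 records a protocol revision of 10/16/2017 that added a study-specific AE definition, and that section is not in the supplied protocol. The SAP also makes the principal investigator responsible for detecting and reporting events. The finding is therefore about what these documents state, not about what was done. A definition alone would still not supply a collection point after month 6.

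**Timing.** The SAP carries revisions dated 2022, after journal review, and reports one-year driving records as already collected by 1/11/2021. Follow-up is probably finished, which affects the fix but not the need to describe ascertainment correctly.

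**The schedule table.** Its layout has been flattened, so the exact span of the continuous AE row cannot be seen. It is laid out like the DriveCam and driving-record rows.

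**Conclusion.** The point holds in this form. The documents state one active AE question, asked at assessment visits, and the last in-person assessment is at month 6. The final 165 to 180 days, 43% to 50% of follow-up, therefore have no stated AE or SAE question, while the SAP describes continuous monitoring and by-arm tables for all randomized teens. The partial sources reach some crashes; they do not systematically reach hospitalizations, non-crash SAEs or deaths.

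The percentages measure time, not events, and rest on the SAP's target days and its month-6 upper bound. The conclusion also assumes that the 12-month survey contains no more than the instruments listed. If an AE item or a later contact was used in practice, the remedy is to say so in the SAP. The documents do not show that harms were missed or that the arms were ascertained differently.

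**What to change.** - **12-month survey.** Add brief AE/SAE items: injury, emergency visit, hospitalization, and any crash since the last visit. If the survey is not returned, call the parent through the existing retention contacts. The call matters because survey return cannot be assumed: SAP 14.7 had medication status during follow-up for 140 teens out of 152, so 12 were missing. It is also the step that could learn of a death.
- **SAP 6.4.** Replace the continuous entry for AEs with the real collection points, and show the monthly DriveCam crash review as a separate row.
- **SAP 8.2.3.** Say that the camera-equipped group is the denominator for camera-detected crashes only, and that the mortality, SAE and other-AE tables use all randomized teens, as section 11 already states.
- **If follow-up is already complete.** The survey change no longer applies. Reconcile protocol 6.e with SAP 6.4, 8.2.3 and 11, and label each safety table with the period and source of ascertainment, for example AE questions through month 6 and camera-detected crashes through month 12.

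The cost is a few items on a form already being sent, some follow-up calls and small wording changes to the SAP. The downside is a slightly longer survey and reliance on self-report.

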4.1 Preface

Glances away from the roadway, especially those longer than 2 seconds, significantly increase one's risk for a motor vehicle crash (MVC). Teen drivers evidence far more extended glances away from the roadway than experienced drivers. Further, teens with a diagnosis of Attention Deficit/Hyperactivity Disorder (ADHD) emit 3-times more extended glances (defined as ≥ 2 seconds) away from the roadway than neurotypical teens. Driving deficits, such as difficulty maintaining lane

position, observed among teen drivers with ADHD are mediated by elevations in the number of extended glances away from the roadway. Hence, there is a clear need for interventions, particularly one that targets extended glances away from the roadway, to address the driving deficits of teens with ADHD. The randomized controlled trial (RCT) described in this Statistical Analysis Plan (SAP) will test the efficacy of an enhanced FOCAL+ intervention (FOCAL+), which targets reducing the number of extended glances away from the roadway, among teens with ADHD. The public health impact of improving the driving behavior of teens with ADHD cannot be overstated. MVCs are the leading cause of death among teens. The 2- to 3-fold increased risk of MVCs among teens with ADHD significantly contributes to these figures. By targeting teens with ADHD, we are targeting one of the highest risk groups of drivers on the road. Were our interventions to normalize driving among teens with ADHD, the potential impact on rates of MVC injuries and deaths would be substantial.

4.2 Scope of the analyses

This SAP describes the planned analyses for the Improving ADHD Teen Driving study (National Institutes of Child Health and Human Development (NICHD) grant # 5R01HD084430). These analyses will empirically test the effectiveness of the FOCAL+ intervention in comparison to a sham placebo intervention at reducing the frequency of extended eye glances and driving performance during simulated driving and real-world driving outcomes captured by in-car technology.

The planned analyses identified in this SAP will be submitted at the study completion as part of the Final Study Report and future manuscripts.

5 Study Objectives and Endpoints

5.1 Study Objectives

The goal of the proposed research is to empirically test the effectiveness of the FOCAL+ intervention in comparison to a sham intervention at improving visual attention and driving performance in teens with ADHD. Specifically, we will conduct a randomized controlled trial using 152 teens diagnosed with ADHD. Teens will be randomized to receive 5 training sessions of the FOCAL+ intervention or a sham intervention. 1-month and 6-months post-training, teens' driving skills, including frequency of extended eye glances, will be assessed during driving simulation. In addition, at the conclusion of training, a DriveCam camera system in their car will record naturalistic driving. The DriveCam will remain in their car until 12-months post-training. Finally, we will acquire the teen's driving records for the period they are in the study.

Primary Objective: We will examine the effectiveness of the FOCAL+ intervention versus sham intervention at decreasing rates of extended glances away from the roadway and improving driving performance among teens with ADHD at 1-month post-training, and 6-months post-training.

Secondary Objective: We will examine the effectiveness of the FOCAL+ intervention versus sham intervention in decreasing rates of extended glances away from the roadway, frequency of driving events, crashes, and crashes/near crashes as measured by in-car technology (DriveCam) during the 12-months post-training.

